6.7.3. Vital Signs (including body weight)

Observed values and changes from baseline in vital sign parameters will be summarized descriptively for fordadistrogene movaparvovec and placebo by visit. If there are multiple records at any timepoint after the start of infusion on Day 1, the average will be included in the analysis.

Categorical tables including post-baseline values, maximum increases (in blood pressure and pulse rate), and maximum decreases (in blood pressure and pulse rate) will be provided. Additionally, categorical tables will also be provided for the first 7 days of follow-up and the first 30 days of follow-up.

6.7.4. Electrocardiograms

Changes from baseline (QT interval, heart rate, QTcF, PR interval, and QRS complex) in ECG parameters will be summarized descriptively for fordadistrogene movaparvovec and placebo by visit. Additionally, the number (%) of participants with ECG findings of potential clinical concern as defined in [Appendix 2.2.2](#) will be summarized for fordadistrogene movaparvovec and placebo.

6.7.5. Physical Examination and Neurological Examinations

No specific data summaries will be provided for physical or neurological examinations. Any findings considered by the investigator to be 'clinically significant' will be recorded as adverse events and will be included in the adverse event summaries.

6.7.6. Echocardiograms

- Changes from baseline to last observation in echocardiogram parameters will be summarized descriptively for continuous parameters and as number and percent of participants for binary parameters for fordadistrogene movaparvovec and placebo.

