2.2. Safety Objectives and Endpoints

Objectives	Endpoints
To characterize the safety of treatment with fordadistrogene movaparvovec as compared to placebo.	
Incidence, severity and causal relationship of treatment-emergent AEs (TEAEs) (adverse events [AEs] and serious adverse events [SAEs]) through Week 52.
 
Incidence of abnormal laboratory findings and magnitude of change through Week 52.
 
Abnormal and clinically relevant changes through Week 52 in:
 
 • Physical exam; • Neurologic exam;

Objectives	Endpoints
	
 • Weight; • Vital signs; • ECG; • Echocardiogram; • Cardiac MRI • Child Behavior Check List (CBCL).

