6.7.7. Cardiac MRI

Observed values and changes from baseline to last observation in cardiac MRI parameters will be summarized descriptively for fordadistrogene movaparvovec and placebo.

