Appendix 2. Data Derivation Details

Appendix 2.1. Definition and Use of Analysis Visit Windows in Reporting

The below analysis windows will be used for the efficacy parameters. If multiple values are observed within a window, the value closest (and prior) to the target day will be included in the analysis. If multiple values are observed within the same day, the worst value will be included in the analysis.

Efficacy Parameter	Visit label	Target day ¹	Window lower limit	Window upper limit ²
NSAA, actigraphy, ankle range of motion	Week 9	60	50	70
	Week 18	120	100	140
	Week 35	240	200	280
	Week 52	360	300	390
CK levels	Week 1, Day 4	4	2	7
	Week 2, Day 14	14	11	17
	Week 3	21	18	24
	Week 4	28	25	31
	Week 5	34	32	41
	Week 7	48	42	54
	Week 9	60	55	67
	Week 11	74	68	82
	Week 13	90	83	105
	Week 18	120	106	140
	Week 35	240	200	280
Week 52	360	300	390	
Muscle biopsy	Week 52	360	300	390
%pFVC, EQ-5D-Y (proxy), EQ-5D-5L (caregivers of participants)	Week 52	360	300	390
PODCI	Week 35	240	200	280
	Week 52	360	300	390
1. Relative to Day 1 (day of IP administration) 2. If Year 2 Day 1 IP is administered after Day 390, the upper limit for the Week 52 window will be Day 390. If Year 2 Day 1 IP is administered on or prior to Day 390, the upper limit for the Week 52 window will be one day before the day of Year 2 Day 1 IP administration.				

The below analysis windows will be used for the immunogenicity parameters. If multiple values are observed within a window, the value closest (and prior) to the target day will be included in the analysis.

Immunogenicity Parameter	Visit label	Target day ¹	Window lower limit	Window upper limit ²
ADA to mini-dystrophin	Week 2, Day 14	14	2	17
	Week 3	21	18	24
	Week 4	28	25	31
	Week 5	34	32	41
	Week 18	120	100	140
	Week 52	360	300	390

ADA to AAV9	Week 5	34	20	48
	Week 18	120	100	140
	Week 52	360	300	390
NAbs	Week 5	34	20	48
	Week 52	360	300	390
T cell response	Week 9	60	50	70
1. Relative to Day 1 (day of IP administration) 2. If Year 2 Day 1 IP is administered after Day 390, the upper limit for the Week 52 window will be Day 390. If Year 2 Day 1 IP is administered on or prior to Day 390, the upper limit for the Week 52 window will be one day before the day of Year 2 Day 1 IP administration.				

The below analysis windows will be used for the safety parameters. If multiple values are observed within a window, the worst value will be included in the analysis.

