	Week 1, Day 4	4	4	5
	Week 1, Day 6	6	6	6
	Week 1, Day 7	7	7	7
	Week 2, Day 8	8	8	8
	Week 2, Day 9	9	9	9
	Week 2, Day 10	10	10	12
	Week 2, Day 14	14	13	17
	Week 3	21	18	27
	Week 5	34	28	47
	Week 9	60	48	75
	Week 13	90	76	105
	Week 18	120	106	180
	Week 35	240	181	300
		Week 52	360	301
ECGs ^b	Week 1 Day 1	1	1	2
	Week 1, Day 7	7	3	9
	Week 2, Day 14	14	10	17
	Week 3	21	18	27
	Week 5	34	28	47
	Week 9	60	48	75
	Week 13	90	76	105
	Week 18	120	106	180
	Week 35	240	181	300
	Week 52	360	301	390

a: If multiple values are observed within a window, the average of all those values will be used.

b: For quantitative values, if multiple values are observed within a window, the average of all those values will be used. For qualitative values, if multiple visits are windowed, the abnormality flag will be used in generating the incidence of abnormality.

The below analysis windows will be used for viral vector shedding. If multiple values are observed within a window, the largest value will be included in the analysis.

Parameter	Visit label	Target day ¹	Window lower limit	Window upper limit
Viral vector shedding (Whole blood)	Week 1, Day 2	2	2	2
	Week 1, Day 4	4	3	11
	Week 3	21	12	40
	Week 9	60	41	75

Parameter	Visit label	Target day ¹	Window lower limit	Window upper limit
	Week 13	90	76	105
	Week 18	120	106	180
	Week 35	240	181	300
	Week 52	360	301	390
Viral vector shedding (urine and saliva)	Week 1, Day 1	1	1	1
	Week 1, Day 2	2	2	2
	Week 1, Day 4	4	3	5
	Week 1, Day 7	7	6	8
	Week 2, Day 10	10	9	11
	Week 2, Day 14	14	12	16
	Week 3	21	17	25
	Week 5	34	26	47
	Week 9	60	48	75
	Week 13	90	76	105
	Week 18	120	106	180
	Week 35	240	181	300
	Week 52	360	301	390
1. Relative to Day 1 (day of IP administration) 2. If Year 2 Day 1 IP is administered after Day 390, the upper limit for the Week 52 window will be Day 390. If Year 2 Day 1 IP is administered on or prior to Day 390, the upper limit for the Week 52 window will be one day before the day of Year 2 Day 1 IP administration.				

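### Echocardiogram and cardiac MRI changes are summarised only to the last observation, although the safety endpoint covers abnormal changes through Week 52

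*SAP*

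**What the plan says.** Section 2.2 lists, among the safety endpoints, "Abnormal and clinically relevant changes through Week 52 in" several assessments that include vital signs, ECG, echocardiogram and cardiac MRI.

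For echocardiogram, Section 6.7.6 states: "Changes from baseline to last observation in echocardiogram parameters will be summarized descriptively for continuous parameters". Binary parameters get numbers and percentages on the same basis. For MRI, Section 6.7.7 states: "Observed values and changes from baseline to last observation in cardiac MRI parameters will be summarized descriptively". Neither section plans a stated by-visit table or a worst post-baseline value. Appendix 2.1 has no window for either assessment.

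ECG and vital signs are handled differently. Section 6.7.4 says that changes "in ECG parameters will be summarized descriptively for fordadistrogene movaparvovec and placebo by visit", and adds "the number (%) of participants with ECG findings of potential clinical concern as defined in" Appendix 2.2.2, where the classes are defined on the maximum. Section 6.7.3 plans by-visit summaries of vital signs, categorical tables of the largest rises and falls in blood pressure and pulse rate, and separate categorical tables for the first 7 and first 30 days.

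The safety windows in Appendix 2.1 open with a general rule: "If multiple values are observed within a window, the worst value will be included in the analysis". Footnote b departs from it for ECG: "For quantitative values, if multiple values are observed within a window, the average of all those values will be used". Footnote a does the same for vital signs, and Section 6.7.3 adds: "If there are multiple records at any timepoint after the start of infusion on Day 1, the average will be included in the analysis".

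**The concern.** The treatment is a single infusion, and an effect on the heart could come early and resolve. The SAP allows for this with troponin I: it keeps the worst value in each window, plots individual profiles, and marks boys with at least two consecutive post-baseline visits above three times the upper limit of normal. Cardiac structure and function, in contrast, are read as change to one endpoint in time. A fall in LVEF, a wall-motion abnormality or a pericardial effusion that had gone by the last scan would not appear in the planned change tables.

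The last observation also need not fall at the same time in every boy. Section 4 says that Cohort 2 boys found retrospectively to meet exclusion criterion 15 are withdrawn, remain in the Safety Analysis Set and contribute partial data. Change to last observation can therefore compare unequal lengths of follow-up between the arms.

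At stake is whether the echo and MRI tables answer the safety endpoint that Section 2.2 sets.

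**Working it through.** The plan gives no figure to reproduce here. The check is a comparison of the texts, with illustrations on assumed values.

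**1. Echo and MRI: endpoint against summary.** The endpoint covers the period to Week 52. The planned change is (last value - baseline), so intermediate scans do not enter it. Assumed LVEF values: baseline 62%, early scan 48%, last scan 61%.
- Change to last observation: 61 - 62 = -1 point.
- Worst post-baseline change: 48 - 62 = -14 points.

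An effusion present at the early scan and absent at the last is likewise counted as absent.

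**2. When this matters.** With one post-baseline scan, the last and the worst value are the same, and nothing is lost. With two or more, scheduled or for-cause, they can differ. The SAP does not state the echo or MRI schedule, so the number of boys affected cannot be derived from it.

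**3. Does averaging remove early ECG and vital-sign effects?** Windows counted in Appendix 2.1:
- ECG: 10 windows, of which 3 end by Day 17 (Days 1-2, 3-9, 10-17).
- Vital signs: 16 windows, of which 9 end by Day 17; 5 of these are single days (Days 1, 6, 7, 8, 9).

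The early time course is therefore kept. Wide windows come late: the widest is Days 181-300, which is 300 - 181 + 1 = 120 days.

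**4. What averaging can do inside one window.** If one reading has a rise R and k others show no change, the mean rise is R/(k+1). For an assumed QTcF rise of 60 msec:
- k = 0: 60
- k = 1: 30
- k = 2: 20
- k = 3: 15

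The by-visit mean can thus be diluted. The outlier table is affected only if its maximum is taken over window averages. Assumed readings of 430 and 505 msec in one window average (430 + 505)/2 = 467.5 msec. Under that reading a boy would move from the class of at least 500 msec to the class from 450 to below 480 msec.

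**5. Does the text settle this?** No. Appendix 2.2.2 refers to a maximum without naming its source records. Footnotes a and b do not limit averaging to the mean tables. Footnote b keeps abnormality flags, but only for qualitative values; QTcF, PR and QRS are quantitative. The version history in Section 1 records that the exclusion of unscheduled and early termination visits was removed for vital signs and ECG, so a for-cause reading can share a window with a scheduled one.

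**The case against.** The strongest objection is that the echo and MRI point depends on a schedule not shown here. If one scan is planned by Week 52, the last-observation wording may serve only to include early-termination scans, and the loss is confined to boys with extra unscheduled ones. This stands as a limit on size. It does not remove the gap, since the wording itself allows for more than one scan. For MRI, observed values are also planned and could be tabulated by visit, but Section 6.7.7 does not say so.

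A second objection is that cardiac effects can surface elsewhere: troponin I by worst value and individual profile, adverse events with time to onset, and events of interest including a peri-infusion group. This also stands. A reader might infer that the plan could miss a cardiac signal altogether; the documents do not support that. Nor do the troponin windows show that only early injury is sought: they run from Day 2 through the Week 52 window, Days 241-390.

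A third objection concerns ECG and vital signs. From the averaging footnotes a reader might infer that transient effects there are erased. They are not, given the by-visit, maximum-based and early-period tables and the retained qualitative flags. Averaging is also understandable for measures that can be abnormal in either direction, whereas Appendix 2.1 states which direction is worse for each laboratory parameter.

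**Conclusion.** The point holds for echocardiogram and cardiac MRI. The planned change summaries cannot show an abnormality that resolves before the last scan, while the endpoint covers changes throughout the period to Week 52. The size ranges from nothing, with one post-baseline scan per boy, to the whole of a transient change in a boy with several; the -1 against -14 example rests on assumed values. Unequal timing of the last observation is a possibility that follows from Section 4, not a demonstrated imbalance.

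For ECG and vital signs only a clarification remains: which records feed the maximum. The SAP does not say that window averages do, so the shift in QTcF class shown above is a consequence of one possible reading, not a planned result. No efficacy analysis or error rate is touched.

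**What to change.** In Sections 6.7.6 and 6.7.7, add:
- summaries by visit;
- the worst post-baseline value through Week 52: lowest LVEF, worst strain, any post-baseline wall-motion abnormality or pericardial effusion, and any increase in the number of LGE-positive segments;
- the last observation as an additional column, with a definition that ties it to the reporting period in Section 2.3.2.

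In Sections 6.7.3 and 6.7.4 and footnotes a and b of Appendix 2.1, limit averaging to the by-visit mean tables. State that the maximum-based classes in Appendix 2.2.2 and the categorical and maximum-change vital-sign tables use individual post-baseline readings, including unscheduled ones.

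The cost is SAP wording and a few extra tables from data already collected. Worst values become more extreme as the number of scans grows, so for-cause scans should be footnoted.

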6.7.7. Cardiac MRI

Observed values and changes from baseline to last observation in cardiac MRI parameters will be summarized descriptively for fordadistrogene movaparvovec and placebo.

6.7.8. Child Behavior Check List (CBCL)

Number and percentage of participants will be presented for each of the following variables for fordadistrogene movaparvovec and placebo:

- Withdrawn T-score or Withdrawn/Depressed Syndrome T-Score ≥ 65 ;
- Internalizing Global Scale T-Score ≥ 60 .

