2.3.2. Treatment Groups and Reporting Periods for Analysis

In the study schematic in Figure 1, the study period and treatment groups to be included in the primary analysis are encircled in red.

- Treatment groups:
 1. fordadistrogene movaparvovec – participants randomized to Cohort 1 to receive a single dose of fordadistrogene movaparvovec on Day 1 (Year 1 Day 1).
 2. Placebo – participants randomized to Cohort 2 to receive a single dose of placebo on Day 1 (Year 1 Day 1).

- Reporting Period:

All analyses will be relative to Day 1 (Year 1 Day 1) investigational product (IP) administration.

The reporting period will include all data from the day of the Year 1 Day 1 IP administration through Week 52. Specifically, all participant data from Day 1 to the earliest of (1) Day 390 (the upper limit of the Week 52 analysis visit window or (2) one day before the Year 2 Day 1 IP administration.

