3.5. Safety Endpoints

For safety endpoints, unless otherwise specified, Baseline is defined as the last non-missing assessment collected prior to Day 1 (Year 1 Day 1) IP administration. For vital signs, baseline is defined as the assessment collected prior to dosing (0 minutes) on Day 1.

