Myocardial strain measures the degree of myocardial deformation from relaxed to contractile state and is expressed as a percentage. Following the different directions in which the myocardium deforms, longitudinal, circumferential and radial strain can be calculated. Longitudinal strain represents the longitudinal shortening from the base to the apex, and it is expressed by negative values. Circumferential strain represents the shortening along the circular perimeter, and it is consequently represented by negative values. Radial strain is the thickening myocardial deformation towards the center of the left ventricular cavity, and it is expressed by positive values.

- Myocardial fibrosis as assessed by number of LGE positive segments

Participants who have a contraindication to the use of gadolinium will be allowed to have an MRI without contrast. In this case, number of LGE positive segments will be missing.

7. Child Behavior Check List (CBCL)

The Child Behavior Check List (CBCL) is a questionnaire designed to assess behavior problems and social competency in children. There are two versions: the 100-item pre-school questionnaire for ages 1.5 to 5 years, and the 120-item school-age questionnaire for ages 6 to 18 years. For this study, scores on the Withdrawn (pre-school) or Withdrawn/Depressed (school-age) syndrome scale and on the Internalizing global scale (both versions) will be examined as high-risk behaviors or dysfunction. Higher scores on the CBCL indicate higher levels of problematic behaviors or dysfunction. The CBCL scoring algorithm allows for a participant's scores to be standardized using scores from a normal population. These standardized scores are referred to as T-scores. A threshold of ≥ 65 on the T-scores for the Withdrawn and Withdrawn/Depressed syndrome scales and a threshold of ≥ 60 on the and Internalizing global scale indicate clinically significant behaviors.

The specific binary endpoints to be assessed are:

- Withdrawn T-score or Withdrawn/Depressed Syndrome T-Score ≥ 65 ;
- Internalizing Global Scale T-Score ≥ 60 .

8. Investigational Product Administered

The three endpoints below will be used to describe the amount of IP administered.

- The actual total administered dose of fordadistrogene movaparvovec in vg will be calculated as

$$\begin{aligned} &\text{Actual total administered dose (vg)} \\ &= \text{planned dose (vg)} * \frac{\text{administered volume (ml)}}{\text{planned volume (ml)}} \end{aligned}$$

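### The CBCL table counts boys at or above a T-score cut without baseline status, so newly emergent cases cannot be told from pre-existing ones

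*SAP*

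**What the plan says.** Section 2.2 states the safety endpoint for a list of assessments as "Abnormal and clinically relevant changes through Week 52 in", and the CBCL is the last item on that list.

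Section 3.5.3 (item 7) explains that raw scores are standardised against a normal population ("These standardized scores are referred to as T-scores") and that the chosen thresholds mark clinically significant behaviour. It then narrows the analysis: "The specific binary endpoints to be assessed are" a withdrawn-type score at or above 65 and an internalizing score at or above 60.

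Section 6.7.8 is the whole analysis: "Number and percentage of participants will be presented for each of the following variables for fordadistrogene movaparvovec and placebo". The two variables are "Withdrawn T-score or Withdrawn/Depressed Syndrome T-Score ≥ 65" and "Internalizing Global Scale T-Score ≥ 60". The section names no visit, baseline column, change or shift, and no restriction to boys below the cut before dosing.

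Two general rules bear on this. Section 3.5 says that, for safety endpoints, "Baseline is defined as the last non-missing assessment collected prior to Day 1 (Year 1 Day 1) IP administration" unless otherwise specified. Section 2.3.2 says "The reporting period will include all data from the day of the Year 1 Day 1 IP administration through Week 52".

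**The concern.** The endpoint has two parts, abnormal findings and clinically relevant changes. A count above a cut serves the first part. It does not serve the second, because change needs a starting point and the table has none.

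For a safety reader, the useful quantity is how many boys without a clinically significant score before dosing acquired one afterwards. The planned table mixes those boys with boys whose score was already high and stayed high. It also leaves no trace of a boy who worsens from an already high score. What is at stake is how a raised or unequal percentage would be read: as emergent behaviour, or as baseline status carried forward.

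**Working it through.** **1. No figure to reproduce.** The SAP states no prevalence, test or sample size for the CBCL. The check is mainly a comparison of sections.

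**2. Does another section supply the baseline?** No.
- Sections 3.4.2 and 6.6.1 (baseline variables and summaries) do not list the CBCL.
- Appendix 2.1 has no CBCL analysis window.
- Section 3.5 defines a safety baseline, but 6.7.8 does not use it.

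**3. How does the plan treat comparable safety data?**
- 6.7.2: laboratory abnormalities, also threshold-based, are reported three ways: regardless of baseline, with normal baseline, and with abnormal baseline. GLDH, GGT, platelets and troponin I also have shift tables.
- 6.7.3 and 6.7.4: vital signs and ECG include change from baseline.
- 6.7.6 and 6.7.7: echocardiogram and cardiac MRI include change from baseline to last observation.
- 6.7.8: CBCL has a status count only.

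**4. What the cell can hide.** Suppose 10 of 66 boys are at or above a cut after dosing, 10/66 = 15.2%. The cell is the same if all 10 were above the cut before dosing (0 new cases) or if none were (10 new cases). Adding a baseline percentage would help, but two marginal percentages still do not show who crossed.

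**5. How many boys could start above a cut (illustration).** Arm sizes are about 66 and 33 (Section 2.3). They are approximate here because the Safety Analysis Set also includes siblings and boys meeting exclusion criterion 15 (Section 4). The baseline prevalence b is an assumption. Expected number = n × b. Chance SD of the between-arm difference = √[b(1−b)(1/66 + 1/33)].

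| b | Active (66) | Placebo (33) | Chance SD |
|---|---|---|---|
| 5% | 3.3 | 1.7 | 4.6 points |
| 6.7% | 4.4 | 2.2 | 5.3 points |
| 15.9% | 10.5 | 5.2 | 7.8 points |
| 30% | 19.8 | 9.9 | 9.8 points |

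The middle rows are what T-scores with mean 50 and SD 10 would give at the two cuts: 1−Φ(1.5) = 6.7% at 65 and 1−Φ(1.0) = 15.9% at 60. The SAP does not state that mean and SD.

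**6. What share of the post-dose count would be pre-existing?** The reporting period starts with dosing, so a boy high beforehand counts only if he is still high afterwards. Take one post-baseline score, SD 10 at both times, baseline mean 50, post-dose mean 50 + s, and correlation r. Share = P(both scores at or above the cut) / P(post-dose score at or above the cut), from the bivariate normal distribution.

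| Shift s | Cut 60, r = 0.6 | Cut 65, r = 0.6 |
|---|---|---|
| 0 | 46% | 34% |
| 5 | 35% | 24% |
| 7 | 32% | 21% |

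Over the same six cases the range is 15% to 34% for r = 0.4 and 27% to 62% for r = 0.8. The pre-existing share is far from negligible throughout, and the planned table cannot recover it.

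**The case against.** The binary form is deliberate. Section 3.5.3 prespecifies it and ties the cuts to clinical significance, and a count above a clinical cut answers the abnormal half of the endpoint. Randomisation balances baseline status in expectation, so the comparison between arms is not systematically biased. The wording in Section 2.2 also covers a list and does not promise a change table for each item: physical and neurological examinations get no summary of their own (6.7.5). All of this stands. It limits the point to missing within-boy information and chance imbalance in small groups.

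The continuous score is not a clean alternative. Section 3.5.3 describes a 100-item form for ages 1.5 to 5 and a 120-item form for ages 6 to 18, and the boys enter at 4 to under 8. Some will change form within the year, so a mean change can mix two instruments. This stands too, and is why the shift table comes first.

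A reader might infer that dichotomising costs the trial a stated amount of power. The documents do not support that framing: 6.7.8 plans no test and no p-value, and no CBCL hypothesis is stated. The power of an unplanned test is not a property of this plan.

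**Conclusion.** The point holds in limited form. Followed exactly, 6.7.8 gives abnormal status by arm and cannot separate emergent from persistent cases, although Section 2.2 names changes and 6.7.2 already makes this split for laboratory abnormalities. No other section fills the gap.

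Its size depends on a baseline distribution that the SAP does not give. Under the assumed 5% to 30%, about 3 to 20 boys on active and 2 to 10 on placebo start above a cut, with a chance difference between arms of about 5 to 10 percentage points (1 SD).

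Two stronger conclusions are tempting and should not be drawn. One is that pre-dose cases dominate the table. With r = 0.6 they are a minority in every scenario examined (21% to 46%); they exceed half only with no shift and a correlation as high as 0.8 (62% at the cut of 60, 52% at 65). The other is that the safety objective cannot be answered for behaviour. That objective is to characterise safety against placebo, and abnormal status compared between randomised groups does address it. What is missing is the change component.

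**What to change.** In Section 6.7.8, keep the planned counts and add, by arm and for each of the two binary variables:

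- a shift table of baseline status (below the cut, at or above the cut) against worst post-baseline status through Week 52, using the baseline already defined in Section 3.5;
- the number and percentage newly at or above the cut, with boys below the cut at baseline as the denominator.

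As a secondary descriptive addition, summarise observed T-score and change from baseline, with change shown separately for boys who stayed on the same CBCL form and boys who switched.

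The cost is SAP wording and one or two extra tables. Emergent counts will be small and should be read descriptively. The SAP does not show the CBCL assessment schedule, so the sponsor should confirm from the protocol that a pre-dose CBCL is collected. If there is only one post-baseline assessment, worst status is simply status at that visit.
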